4.5 VISIT WINDOWS

In general, data for assessments that are collected by scheduled visits will be mapped to visits that appear in the schedule of assessments ([Appendix 2](#)) per the protocol using the actual study day of assessment. Data mapped to scheduled visits will include all data collected up to the final database lock, and may include withdrawal visits and unscheduled visits. Data will never be mapped to visits for which the assessment was not scheduled in the protocol (i.e., results for an assessment conducted at an unscheduled visit will be mapped to the appropriate visit at which the assessment was scheduled). Visit windows will be continuous from the midpoint between two consecutive study visits, and will be dependent on the schedule of assessments for each variable independently. An example of the urinalysis visit window is given in [Table 1](#). Visit windows for each variable will be constructed in the same manner.

Table 1 Time Windows of Study Days to Assign Study Visit for Urinalysis

Study Visit	Scheduled Study Day	Actual Study Day Time Window
Baseline	1	≤ 1
Week 4	28	$2 \leq \text{day} < 57$
Week 12	84	$57 \leq \text{day} < 127$
Week 24	168	$127 \leq \text{day} < 211$
Week 36	252	$211 \leq \text{day} < 309$

Week 52	364	309≤day<425
Week 76	532	425≤day<631
Week 104	728	631≤day<789
BCFU	>789	

BCFU=B-cell follow up

Derived variables that are collected on an ongoing basis will be presented using appropriate time intervals. For primary analysis at Week 52, the upper limit of the visit window will be Day 364 + 60 days. For Week 104, the upper limit of the visit window will be 728 + 60 days. For BFU, the visit is scheduled every 6 months.

Data displays that are presented by visit will only include visits at which the assessment was scheduled to be collected. The methods for handling multiple values within a visit window are described in Section 4.9.3.

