4.6.2.2 Biomarkers of Lupus Nephritis

The change from baseline of biomarkers of LN disease activity will be summarized by treatment arm using tables and graphs. These biomarkers may include changes in anti-dsDNA antibody levels and in C3, C4, levels.

Missing Data

Missing data will be imputed using last observation carried forward (LOCF).

4.6.2.3 Complete Renal Response at Week 24

The proportions of patients who achieve a CRR will be analyzed using similar methodology as the primary analysis.

Missing Data for Serum Creatinine at Week 24

Missing serum creatinine at Week 24 will be imputed using the value from Week 12 first, and if still missing, then take the value from Week 26. If still missing then, no imputation will be made.

Missing Data for Inactive Urinary Sediment at Week 24

Missing data will be imputed using the same method specified in Section 4.6.1.3 .

Missing Data for UPCR (24-Hour) at Week 24

Missing data will be imputed using the same method specified in Section 4.6.1.4 .

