4.11.2 Renal Response Interim Analysis

The iDMC will also conduct an interim efficacy analysis to evaluate renal response when the last patient has achieved the 6-month visit. The interim analysis will be performed by the iDCC and interpreted by members of the iDMC. The iDMC may recommend to the Sponsor to consider the planning of Phase III if the treatment difference (obinutuzumab minus placebo) in complete renal response at Week 24 is $\geq 10\%$. In addition, the iDMC will inform the Sponsor if the treatment difference (obinutuzumab minus placebo) in complete renal response at Week 24 is $\geq 20\%$.

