Appendix 2 Schedule of Assessments

	Week	Treatment Period								
		−4 to 0	1	2	4	12	24	26	36	52/ET
Day	−28 to −1	1 ^a	15	28	84	168	182	252	364	
Informed consent		x								
Inclusion/exclusion criteria		x	x							
Medical history		x	x							
IxRS assignment ^b		x	x							
Demographic data		x								
Subject's Global Assessment ^c			x		x	x	x		x	x
Physical exam (limited)		x	x				x			x
Height		x								
Vital signs and weight ^d		x	x	x	x	x	x	x	x	
12-Lead ECG		x								x
Chest X-ray ^e		x								
Physician's Global Assessment			x		x	x	x		x	x
SLICC/ACR assessment		x					x			x
SLEDAI-2K		x	x		x	x	x		x	x
Glucocorticoid Toxicity Change Index			x			x	x			x
Hematology ^f		x	x	x	x	x	x	x	x	x
Serum chemistries ^g		x	x	x	x	x	x	x	x	x
Urinalysis ^h		x	x		x	x	x		x	x

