Appendix 2 Schedule of Assessments (cont.)

Week	Day	Treatment Period								
		-4 to 0	1 ^a	2	4	12	24	26	36	52/ET
	-28 to -1									
24-hour urine collection ⁱ		X	X			X	X		X	X
Pregnancy test ^j		X	X	X	X	X	X	X	X	X
HBsAg ^k , HBcAb, Hepatitis C antibody		X								
Autoantibody profile ^l		X	X		X	X	X		X	X
Antibody titers ^m		X					X			X
Serum PK sampling ⁿ			X ⁿ	X ⁿ	X	X	X ⁿ	X ⁿ	X	X
Blood sample for flow cytometry ^o			X	X	X	X	X ^o			X
Serum ADAs			X ^o				X ^o			X
Quantitative serum Ig levels (total, IgG, IgM, and IgA)		X	X			X	X			X
C3, C4, CH50 complement		X	X	X	X	X	X		X	X
Serum for biomarkers ^o		X	X ^o	X	X	X	X ^o		X	X
Plasma for biomarkers ^o		X	X ^o	X	X	X	X ^o		X	X
Urine for biomarkers ^{p, o}		X	X	X	X	X	X		X	X
PAXgene RNA ^o		X	X ^o	X	X	X	X ^o		X	X
Blood DNA ^q (optional)		X								
Record of menses		X	X	X	X	X	X	X	X	X
Adverse events ^r			X ^r	X ^r	X	X	X ^r	X ^r	X	X

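### Week 24 CRR: a late visit's creatinine is mapped to Week 26 while its urine stays at Week 24, and the fill rule then prefers the Week 12 creatinine

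*SAP*

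**What the plan says.** SAP 4.5 sets the mapping rule: "Visit windows will be continuous from the midpoint between two consecutive study visits, and will be dependent on the schedule of assessments for each variable", taken independently. It prints one example, Table 1 for urinalysis, in which Week 24 is 127 ≤ day < 211, and adds: "Visit windows for each variable will be constructed in the same manner". It also says: "Data will never be mapped to visits for which the assessment was not scheduled in the protocol".

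The schedule of assessments (SAP Appendix 2, the same as Protocol Appendix 1) has serum chemistries on Days 84, 168, 182 and 252. Urinalysis and the 24-hour urine collection are on Days 84, 168 and 252, with nothing on Day 182.

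For a missing Week 24 creatinine, SAP 4.6.2.3 says: "Missing serum creatinine at Week 24 will be imputed using the value from Week 12 first, and if still missing", the Week 26 value is taken; after that nothing is imputed. Week 24 sediment and urine protein to creatinine ratio (UPCR) follow 4.6.1.3 and 4.6.1.4. Those sections try other sources at the same visit before going back one visit.

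Week 24 CRR is twelfth and last in the testing order in SAP 4.6. It is also the measure in SAP 4.11.2, where the data monitoring committee's advice on planning turns on differences of at least 10% and at least 20%.

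**The concern.** CRR needs creatinine, sediment and UPCR to meet their criteria together. Nothing in the SAP requires the three to share a date or to lie within a maximum interval. Because creatinine has an extra scheduled visit two weeks after Day 168, the mapping rule can give one visit's blood and urine different labels. The fill rule then treats the creatinine as missing and goes back to Week 12, although a central value from the same day is in the database.

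An outdated creatinine could change a patient's Week 24 status in either direction. Elsewhere the SAP favours closeness: 4.9.3 takes the value nearest the nominal day, and the urine components use same-visit sources first. SAP 4.6.2.3 already accepts Week 26 as a substitute but ranks it second without giving a reason.

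**Working it through.** **Inputs.** Window rule and Table 1: SAP 4.5. Schedules: SAP Appendix 2. Fill order: SAP 4.6.2.3. Visit tolerance of ±3 days: notes to the schedule of assessments. Planned 60 per arm: SAP 2.3.

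**Step 1: reproduce the printed windows.** First day = midpoint with the previous scheduled day, rounded down, plus 1. Last day = midpoint with the next scheduled day, rounded down. For urinalysis (Days 28, 84, 168, 252, 364):

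- Week 12: (28+84)/2 = 56 and (84+168)/2 = 126, giving Days 57-126.
- Week 24: (168+252)/2 = 210, giving Days 127-210.
- Week 36: (252+364)/2 = 308, giving Days 211-308.

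All three agree with Table 1.

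**Step 2: apply the same rule to the other components.** The SAP does not print these windows; they are derived.

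| Variable | Week 12 | Week 24 | Week 26 |
|---|---|---|---|
| Urinalysis | 57-126 | 127-210 | none |
| 24-hour urine | 43-126 | 127-210 | none |
| Creatinine | 57-126 | 127-175 | 176-217 |

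The creatinine bounds use (168+182)/2 = 175 and (182+252)/2 = 217. Days 176-210 are therefore Week 24 for urine and Week 26 for creatinine.

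**Step 3: late visit.** Suppose urine and creatinine are both taken on one day between 176 and 210, with no creatinine on Days 127-175. The creatinine maps to Week 26, Week 24 creatinine counts as missing, and Week 12 is used. With a Day 84 value the gap to the urine is 176-84 = 92 days to 210-84 = 126 days; for a Day 178 visit it is 178-84 = 94 days. Across the whole Week 12 creatinine window the gap runs from 176-126 = 50 to 210-57 = 153 days. A same-day value, with gap 0, is passed over.

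**Step 4: only the Day 168 creatinine missing.** Week 12 is 168-84 = 84 days away and Week 26 is 182-168 = 14 days away. The farther value is used.

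**Step 5: on-time visits.** 168 ± 3 gives Days 165-171, inside both windows. No split occurs. A split needs a visit at least 176-168 = 8 days late.

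**Step 6: size per patient.** 1/60 = 1.7 percentage points of one arm's Week 24 CRR for each patient reclassified.

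**The case against.** The strongest objection is to simply reversing the order, which a reader might infer is the remedy. If the whole Week 24 visit is missed, 4.6.1.3 and 4.6.1.4 send sediment and UPCR back to Week 12, and no Week 26 urine is scheduled. The current rule then keeps all components at Week 12. Week 26 first would pair Day 182 creatinine with Day 84 urine, 182-84 = 98 days apart, which is worse than the 84 days criticised. Widening the creatinine window to Days 127-210 does the same, because Day 182 falls inside it. This objection stands, and it limits the fix to cases where Week 24 urine exists.

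Week 12 first also agrees with the previous-visit rule in SAP 4.6.1.2, so this is not an internal contradiction. A rationale is available too: Week 24 samples are taken before the Day 168 infusion and Day 182 samples after it. The SAP does not give that reason, and it does not apply to a late visit whose blood and urine were both drawn before a delayed infusion.

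A split also requires a departure from the visit tolerance. That is true, but late visits are foreseeable: Day 168 is an infusion visit, and Protocol Table 6 has study drug withheld during an active infection until it resolves.

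Finally, a reader might infer that the interim planning decision or the time-to-response endpoints are compromised. The documents do not support either. This SAP version covers the final clinical study report, after the Week 52 and Week 104 reports, so it cannot alter a past interim decision, and that interim was for planning only. The Week 12/Week 26 fill rule is written for Week 24 CRR alone. SAP 4.6.2.1 refers missing data to 4.6.1, so at most the visit mapping carries over to time to response.

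**Conclusion.** The concern holds in a limited form. Read together, SAP 4.5 and 4.6.2.3 can discard a central creatinine drawn with the Week 24 urine and use one about three months older: 92-126 days if the Week 12 value is from Day 84. When only the Day 168 creatinine is missing, they rank a value 84 days away above one 14 days away. This rests on the derived creatinine window and, for the split visit, on there being no creatinine on Days 127-175.

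The reach is narrow. On-time visits are not split, the primary Week 52 CRR does not use this fill rule, and no later test depends on Week 24 CRR. The documents do not say how many patients are affected; the number is probably small, and neither the size nor the direction of any bias can be computed. The 1.7 points per patient is a unit, not an estimate of bias. This is a cheap improvement to an analysis rule and does not by itself cast doubt on the Week 24 result.

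**What to change.** In SAP 4.5 and 4.6.2.3, for Week 24 CRR:

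1. When Week 24 urine is available, use the central creatinine drawn on the same date as that urine before any imputation, even if that day falls in the Week 26 creatinine window. Name which urine sample sets the date, for instance the UPCR sample.
2. When Week 24 urine exists but there is no same-date creatinine, keep the current rule in the main analysis and add a sensitivity analysis using the creatinine nearest in time to the urine, with Week 26 before Week 12.
3. When the Week 24 urine is itself filled from Week 12, keep the Week 12 creatinine so that the components stay together.

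Report how many patients in each arm fall under each case.

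The cost is a few sentences and a small programming change, with no new data. Because the Week 52 and Week 104 reports already exist, the change should be labelled post hoc and its result shown beside that of the current rule.

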4.6.2.4 Modified Complete Renal Response

In addition, the modified definitions, mCRR1, mCRR2, and mCRR3 of CRR will be analyzed to assess the sensitivity of CRR to its definition.

- Proportion of patients who achieve a modified CRR (mCRR1) at Week 52 employing the primary–efficacy measure definition and removing the urinary sediment analysis criteria.

mCRR1 is defined by attainment of normalization of serum creatinine as evidenced by the following:

- Serum creatinine \leq the ULN range of central laboratory values if baseline (Day 1) serum creatinine is above the ULN
- Serum creatinine \leq 15% above baseline and \leq the ULN range of central laboratory values if baseline (Day 1) serum creatinine \leq the ULN range of central laboratory values
- Urinary protein to creatinine ratio <0.5

- Proportion of patients that achieve a second modified CRR (mCRR2) at Week 52 as defined by attainment of the following:

- Serum creatinine \leq 15% above baseline if baseline (Day 1) serum creatinine is above the normal range of the central laboratory values
- Serum creatinine \leq the ULN range of central laboratory values if baseline (Day 1) serum creatinine is \leq the ULN range of central laboratory values
- Inactive urinary sediment (as evidenced by <10 RBCs/HPF and the absence of red cell casts)
- Urinary protein to creatinine ratio <0.5

- Proportion of patients that achieve a third modified CRR (mCRR3) at Week 52 as defined by attainment of the following:

- Serum creatinine \leq the ULN range of central laboratory values
- Urinary protein to creatinine ratio <0.5

Missing Data

Missing data for each component of the endpoint will be imputed using the relevant approach discussed in Section 4.6.1.1.

4.6.3 Exploratory Efficacy Endpoints

The following endpoints will provide additional information to assess treatment efficacy.

4.6.3.1 Urine protein creatinine ratio (UPCR)

Absolute value at each visit and change from baseline in UPCR over 104 weeks will be presented in each arm using summary statistics to evaluate the trends over time.

4.6.3.2 Renal Flares

Proportion of patients experiencing a renal flare over 52 weeks and 104 weeks. This will be summarized using frequency counts and percentages.

4.6.3.3 Physician's Global Assessment (PGA)

Absolute value at each visit and change from baseline in PGA over 52 weeks will be presented in each arm using summary statistics to show the trends over time.

4.6.3.4 Subject's Global Assessment (SGA)

Absolute value at each visit and change from baseline in SGA over 52 weeks will be presented in each arm using summary statistics to show the trends over time.

4.6.3.5 Components of CRR

Proportion of patients achieving each of the components of the primary endpoint will be present by each visit over 104 weeks. This will be summarized using frequency counts and percentages.

4.7 PHARMACOKINETIC AND PHARMACODYNAMIC ANALYSES

Pharmacokinetic (PK) parameters have been determined for all patients with serum concentration data in the previous CSRs. A list of PK and ADA values will be presented in the final CSR.

The primary pharmacodynamic (PD) marker will be CD19⁺ B-cell counts. Exploratory PD markers from blood samples may be summarized graphically and descriptively over time by treatment arm.

In addition, the percent change from baseline for each marker will be computed at each sampling timepoint using the Day 1 pre-dose value as the baseline point.

Exploratory analyses may be performed to assess the possible relationship between obinutuzumab dosing, PD markers, PK measures, and clinical response.

4.8 SAFETY ANALYSES

The safety analysis will be performed on the safety population as defined in Section 4.1.3. Analyses of safety data will include patients up to the point of receipt of non-corticosteroid rescue only. All safety data including the post-rescue data will be summarized separately for key safety outputs.

All safety outputs will include cumulative data to the final database lock. In addition, data collected after Week 104 will be summarized separately for key safety outputs to understand the Safety events occurring during the B-cell follow-up period only. Safety data will be summarized by treatment groups.

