### LENGTH OF STUDY

The study will follow all patients for a minimum of 78 weeks after the last infusion of obinutuzumab at Day 182. In consideration of recruitment and follow-up (independent of B-Cell follow-up [BCFU]), the length of study is estimated to be greater than 36 months. Patients may enter BCFU and continue to be evaluated for safety on a limited basis.

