### END OF STUDY

The end of this study is defined as the last patient's last visit at Week 104. This has been selected to enable 78 weeks (~18 months) of safety follow-up after the last dose of study drug to assess the occurrence of adverse events and to enable an assessment of peripheral blood CD19+ B cell return.

Additional B-cell follow-up (BCFU) visits will occur until patients have achieved their baseline CD19+ count or achieved 25 cells/ $\mu\text{L}$  CD19+ count (the lower limit of normal (LLN) of CD19+ B cells for this lupus population), whichever occurs first. B-cell follow-up (BCFU) visits for all patients will end when the last patient has completed ~18 months of safety follow-up from the last dose of blinded obinutuzumab infusion.

Patients who receive additional therapies that reduce peripheral B-cell counts will not be included in BCFU.

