### **3.2 END OF STUDY**

*The end of this study is defined as the last patient's last visit at Week 104. This has been selected to enable 78 weeks (~18 months) of safety follow-up after the last dose of study drug to assess the occurrence of adverse events and to enable an assessment of peripheral blood CD19+ B cell return.*

*Additional B-cell follow-up (BCFU) visits will occur until patients have achieved their baseline CD19+ count or achieved 25 cells/µL CD19+ count (the lower limit of normal (LLN) of CD19+ B cells for this lupus population), whichever occurs first. B-cell follow-up (BCFU) visits for all patients will end when the last patient has completed ~18 months of safety follow-up from the last dose of blinded obinutuzumab infusion.*

*Patients who receive additional therapies that reduce peripheral B-cell counts will not be included in BCFU.*

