#### **5.3.1 Adverse Event Reporting Period**

Investigators will seek information on adverse events at each patient contact. All adverse events, whether reported by the patient or noted by study personnel, will be recorded in the patient's medical record and on the Adverse Event eCRF.

**After informed consent** has been obtained **but prior to initiation of study drug**, only serious adverse events caused by a protocol-mandated intervention (e.g., invasive procedures such as biopsies, discontinuation of medications) should be reported (see Section 5.4.2 for instructions for reporting serious adverse events).

**After initiation of study drug**, all adverse events, regardless of relationship to study drug, will be reported until the patient completes his or her last study visit at Week 104 or for a period of 76 weeks after the last dose of study drug (whichever is longer). After this period, the investigator should report any serious adverse events that are believed to be related to prior study drug treatment (see Section 5.6).

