4.4 DATA-CUT FOR ANALYSES

All data in the final database will be reported, unless otherwise specified in the relevant sections of the SAP.

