4.8.2 Adverse Events

Adverse events will be mapped and reported using the Medical Dictionary for Regulatory Activities (MedDRA) thesaurus using the most current version at the time of analysis (Version 20.1 or later). Glossaries showing the mapping of investigator verbatim terms to coded events will be produced.

Treatment-emergent adverse events (TEAEs) will be summarized. All AEs referenced in the section below will be TEAEs. TEAEs are defined as those AEs with observed or imputed onset date on or after the start date of trial treatment. Only where the most extreme intensity is greater than the initial intensity (or if most extreme intensity is not missing and initial intensity is missing) will events with an onset date prior to the start of trial treatment be considered treatment-emergent. An AE with a completely missing start date will be assumed to be treatment-emergent unless the AE has a complete non-imputed end date that is prior to study Day 1.

Listings will show all AEs reported, including AEs occurring after rescue therapy, and any AEs that may have occurred during the oral corticosteroid dose adjustments in the screening period.

AEs will be summarized by system organ class (SOC) and preferred term (PT), and will be presented in order of descending frequency summed across the treatment arms within each SOC and PT.

The following will be summarized, and/or listings produced where required:

- All AEs
- Serious Adverse Events (SAEs)
- AEs by relationship to obinutuzumab/placebo
- AEs by relationship to MMF/MPA
- Corticosteroid-related adverse events
- AEs leading to study drug dose modification or interruption
- AEs by common terminology criteria grade
- Infections
- Serious Infections
- Infusion related reactions (IRRs)
- Serious IRRs

Obinutuzumab—F. Hoffmann-La Roche Ltd

Statistical Analysis Plan

WA29748

- AEs leading to withdrawal
- AEs leading to death

AEs to monitor will be listed, including:

- Opportunistic infections (Roche Standard AE Grouped Term [AEGT] Basket)

AE rates per 100 patient-years exposure will be produced for key safety events. Rates will be based on all occurrences of AE. AE rate per 100 patient-years is defined as:

$$(\text{number of events} \div \text{total exposure}) \times 100$$

The 95% confidence intervals (CIs) will be calculated based on exact poisson distribution.

Positive pregnancy results will be listed, as identified using the serum test results.

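### By-arm safety tables in the final CSR accumulate to database lock, although follow-up after Week 104 depends on B-cell recovery and so on the drug's own effect

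*SAP*

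**What the plan says.** SAP Section 4.8 sets the data cut for safety: "All safety outputs will include cumulative data to the final database lock". It presents safety data by treatment group. SAP Section 4.4 applies no other limit: "All data in the final database will be reported, unless otherwise specified in the relevant sections of the SAP". SAP Section 4.8.2 bounds events only from below: "TEAEs are defined as those AEs with observed or imputed onset date on or after the start date of trial treatment". Categorical results are numbers and percentages of patients (SAP Section 4.9.1), and SAP Section 4.8.4.1 adds shift tables to the highest post-baseline grade.

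The common follow-up is fixed in the protocol synopsis, Length of Study: "The study will follow all patients for a minimum of 78 weeks after the last infusion of obinutuzumab at Day 182". What follows depends on the patient's B cells. Protocol Section 3.2 says: "Additional B-cell follow-up (BCFU) visits will occur until patients have achieved their baseline CD19+ count", or 25 cells/µL if that comes first. B-cell follow-up (BCFU) also has a calendar end, because "visits for all patients will end when the last patient has completed ~18 months of safety follow-up from the last dose of blinded obinutuzumab infusion". Protocol Appendix 2 schedules adverse events, chemistries and immunoglobulins at the six-monthly BCFU visits.

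The SAP offers two partial remedies. One is that "data collected after Week 104 will be summarized separately for key safety outputs to understand the Safety events occurring during the B-cell follow-up period only". The other is rates per 100 patient-years for key safety events (Section 4.8.2).

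**The concern.** A percentage of patients with at least one event can only rise with observation time, and so can a worst post-baseline grade. If one arm is watched for longer, it shows more events even when the true rates are equal. Here the extra time is not random. A patient leaves BCFU on B-cell recovery, and obinutuzumab is given to deplete B cells. The comparison in the final CSR is thus tilted by a consequence of treatment, for outcomes such as infections and serious infections where the comparison matters most.

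Patient-year rates do not fully repair this. They cover key events only, and their denominator is unclear: SAP Section 4.8.2 divides by total exposure, while SAP Section 4.8.1 relies on an exposure date said to be defined in Section 4.2, which defines none.

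The collection rule also differs by section. Protocol Section 5.3.1 requires all adverse events until the later of Week 104 and 76 weeks after the last dose, and then: "After this period, the investigator should report any serious adverse events that are believed to be related to prior study drug treatment". Protocol Section 5.4.2.2 gives 52 weeks after the last dose for serious events and events of special interest. Appendix 2 still lists adverse events at every BCFU visit.

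**Working it through.** **The plan's own figure.** The last infusion is on Day 182 and Week 104 is Day 728. (728 − 182)/7 = 78.0 weeks, which reproduces the stated minimum. Two other windows on the same scale, for a patient dosed on schedule:
- 76 weeks after Day 182 is 182 + 532 = Day 714 (Week 102), so the Section 5.3.1 period ends at Week 104.
- 52 weeks after Day 182 is 182 + 364 = Day 546 (Week 78), so the Section 5.4.2.2 window closes 26 weeks earlier.

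**Inputs for the size.** From the documents: 60 patients per arm and about 2.0 years to Week 104. Assumed, because the documents do not give them: the event rate h, equal in both arms and constant; the fraction f of the obinutuzumab arm in BCFU (placebo taken as 0); and the extra years L. Dropout and rescue are ignored.

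**Formulas.**
- Placebo: 1 − exp(−2h)
- Obinutuzumab: (1 − f)(1 − exp(−2h)) + f(1 − exp(−(2 + L)h))
- Spurious excess: f × [exp(−2h) − exp(−(2 + L)h)]

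**Worked cases at h = 0.10 per year.** Placebo is 1 − exp(−0.2) = 18.1%.
- f = 5%, L = 1: 0.05 × (0.8187 − 0.7408) = 0.4 points (18.5% against 18.1%).
- f = 10%, L = 2: 0.10 × (0.8187 − 0.6703) = 1.5 points (19.6% against 18.1%). On 60 patients, 0.015 × 60 = 0.9 of a patient.

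**Range of the spurious excess, in percentage points.**

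| f, L | Patient-years, obinutuzumab vs placebo | h = 0.05 | h = 0.10 | h = 0.30 |
|---|---|---|---|---|
| 5%, 1 year | 123 vs 120 | 0.2 | 0.4 | 0.7 |
| 10%, 2 years | 132 vs 120 | 0.9 | 1.5 | 2.5 |
| 20%, 2 years | 144 vs 120 | 1.7 | 3.0 | 5.0 |
| 40%, 3 years | 192 vs 120 | 5.0 | 8.5 | 13.0 |

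**Which rows are plausible.** The Version 4 amendment rationale reports that the vast majority of patients in this study had recovered or repleted B cells by 18 months after the last dose, which is about Week 104, and that a small percentage stayed depleted. That points to the upper rows. One caution applies. Repleted is not a defined term. Protocol Section 5.1.6 sets repopulation at 10 cells/µL, a lower bar than the 25 cells/µL or baseline count needed to leave BCFU. If repleted means repopulated, more patients could remain in BCFU than the sentence suggests.

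**Patient-year rates.** Take a front-loaded rate that is the same in both arms: 0.4 per year for 6 months, then 0.05 per year.
- Placebo: (0.4 × 0.5 + 0.05 × 1.5)/2 = 0.275/2 = 13.75 per 100 patient-years.
- Obinutuzumab at f = 10%, L = 2: (0.275 + 0.05 × 0.2)/2.2 = 12.95 per 100 patient-years.

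This assumes that the denominator is follow-up time. The bias then runs the other way, because the added time is low-risk time.

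**After the fix.** With both arms cut at 2.0 years and h = 0.10, both show 18.1% and the spurious gap is 0.

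**The case against.** The best defence is that this SAP governs only the final CSR, whose stated purpose is to report all available data. SAP Section 1 says that Week 52 and Week 104 CSRs have already been reported, and protocol Section 6 places the primary safety analysis at Week 52. The tables are descriptive, from a Phase II study with no safety hypothesis test. Patient duration in the study is summarised (SAP Section 4.2), key post-Week 104 outputs are shown separately, and key events get patient-year rates. BCFU closes for everyone at a common calendar point, so extra time is limited by the enrolment spread and is near zero for late enrollees.

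Most of this stands as a limit on size. It does not correct the cumulative tables: the contents of the Week 104 CSR are not in these documents, and this SAP specifies no safety table through Week 104.

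Several stronger readings are tempting but unsupported:
- A reader might infer an excess of many points by taking 30% to 50% of the arm into BCFU. No passage gives such a fraction, and the amendment rationale points to a small one.
- A reader might infer that BCFU contains almost only obinutuzumab patients. The direction is a fair expectation, but no document gives follow-up by arm, and a placebo patient below both thresholds would also qualify.
- A reader might take every patient as followed to Week 104. The main safety analyses stop at non-corticosteroid rescue (SAP Section 4.8), and withdrawn patients may have only 52 weeks after the last dose (protocol Section 4.6.1).
- A reader might infer a fixed dilution of the patient-year rates, or that late reports are coloured by knowledge of assignment. The first needs a denominator that the SAP does not define; the second is conjecture.

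**Conclusion.** The concern holds as a defect in the final CSR's main safety tables. Cumulative by-arm percentages and worst-grade tables compare periods whose length depends on B-cell recovery, and the remedies in the SAP leave those tables as they are. The expected direction is against obinutuzumab for crude percentages; for patient-year rates it depends on how the event rate changes over time and on the denominator.

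The likely size is modest: about 0.4 to 1.5 points at 10 events per 100 patient-years, for 5% of the arm with 1 extra year up to 10% with 2 extra years. This rests on equal constant rates, 2 years of common follow-up, no placebo patients in BCFU, and a BCFU fraction and length that are assumed. The excess becomes large only if many more patients stayed in BCFU, which the documents neither show nor fully exclude.

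**What to change.** 1. In SAP Section 4.8, make the main between-arm safety tables and rates, including the worst-grade shift tables, stop at a common cut-off: Week 104 or the protocol Section 5.3.1 reporting period, stated as a study day.
2. Report later data separately as descriptive BCFU data, with the number of patients and follow-up time by arm.
3. Define the patient-year denominator as time at risk, and correct the reference in SAP Section 4.8.1 to an exposure date that Section 4.2 does not contain.
4. Reconcile protocol Sections 5.3.1 and 5.4.2.2 and Appendix 2 on what is collected and until when, so that the BCFU denominator has a clear meaning.

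The cost is SAP wording, a date filter and one more set of tables, partly repeating the Week 104 CSR. No event is lost, because SAP Section 4.8.2 already lists all adverse events. The cut at non-corticosteroid rescue remains a separate source of unequal follow-up that this change does not address.
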